2.8 Immunogenicity (IM) Analysis

Samples collected at pre-dialysis/pre-dose on Days 1, 15, 29, 85, 176, and anytime on Day 260, including early termination samples for IM assessment will be analyzed for anti-ISIS 416858 antibodies (ADA). However, plasma samples collected at other time points (for PK purposes) may also be potentially evaluated if deemed of further interest and warranted by the pharmacokinetic scientist. An evaluable sample will be designated 'IM positive' based on both positive screening and confirmation assay results (i.e., confirmed positive result), and otherwise will be deemed 'IM negative'. Sample IM results (screen positive/negative, confirmed positive/negative or unevaluable, and when applicable, titer of anti-ISIS 416858 antibodies) before, during, and after treatment with study drug (ISIS 416858 or placebo) (sample IM status) will be listed by treatment and dose.

Study subjects will be given 'IM positive' status if they have at least one confirmed positive sample result at any time during the treatment or post-treatment evaluation periods. Study subjects will be given 'IM negative' status if all evaluated IM sample results during the treatment and post-treatment evaluation periods are IM negative and they have at least one evaluable IM result collected post study drug treatment. Otherwise, a study patient will be given 'unknown' IM status. Subject IM results will be listed by treatment and dose for all evaluable patients, which will include but may not be limited to: subject JM status (positive, negative or unknown), the study day associated with the first positive TM status emerged (T1ii-s1, i.e., onset of ADA development), the last positive IM status observed (T1as1), the time of last evaluable IM sample collected (T1as1 sampling), peak titer, and time to reach peak titer. The onset of ADA and time to reach peak titer will be calculated by:

- Onset in days= The date of first sample has "positive" sample IM status - first dose date +1;
- Time to reach peak titer in days= The date of first peak titer observed- first dose date +1;

Other immunogenicity data analysis (e.g. classification as transient or persistent status for IM positive subjects) if there is sufficient number of patients with transient IM status. Transient and Persistent ADA definitions are defined below and based on Shankar et al. (2014).

Transient ADA response will be defined as:

- Treatment-induced ADA detected only at one sampling time point during the treatment or follow-up observation period (excluding the last sampling time point, which will be considered persistent unless shown to be undetectable at a later time) or
- Treatment-induced ADA detected at two or more sampling time points during the treatment (including follow-up period if any), where the first and last ADA-positive samples (irrespective of any negative samples in between) are separated by a period less than 16 weeks, and the subject's last sampling time point is ADA-negative.

Persistent ADA response will be defined as:

- Treatment-induced ADA detected at two or more sampling time points during the treatment (including follow-up period if any), where the first and last ADA-positive samples (irrespective of any negative samples in between) are separated by a period of 16 weeks or longer or
- Treatment-induced ADA detected only at the last sampling time point of the study treatment period or at a sampling time point with less than 16 weeks before an ADA-negative last sample.

The sample IM incidence (number) and incidence rate (percent) at each evaluated study time point, and for the overall treatment and post-treatment evaluation period, as well as subject IM incidence and incidence rate, will be determined and appropriately summarized by treatment, as the total number of and percentage of evaluated subjects with IM negative, positive, and unknown status. Subjects with positive IM status may further be classified as transient or persistent status if applicable, and incidence and incidence rate for being transient or persistent will be appropriately summarized. Furthermore, onset, titer over time, and peak titer of the ADA response, if applicable, will be also appropriately summarized (using descriptive statistics) as median, quartiles (25% and 75%), and range and presented graphically, if deemed appropriate, by treatment at the discretion of the designated study pharmacokineticist and/or statistician (e.g., summarized at each evaluated study time point and overall; summarized by observed peak titer values from the individual IM positive subjects; etc.).

In addition to PK assessments (Section 3.7), selected safety (Section 3.3) and efficacy (Sections 3.4 to 3.5) assessments may be further stratified by subject IM status (i.e., subject IM status being positive, negative or unknown) and presented in tables and/or graphically, as deemed appropriate or warranted by the designated study pharmacokineticist, medical monitor, and/or biostatistician. Other stratifications (e.g., based on antibody titer, onset of ADA, etc.) of selected PK, efficacy and safety assessments may also be performed if deemed warranted at the discretion of the pbarmacokineticist, medical monitor, and/or biostatistician.

Official Title: A Phase 2, Randomized, Double-Blind, Placebo-Controlled Study of the Safety, Pharmacokinetics, and Pharmacodynamics of Multiple Doses of ISIS 416858 (IONIS-FXIRX an Antisense Inhibitor of Factor XI), Administered Subcutaneously to Patients with End-Stage Renal Disease on Hemodialysis

NCT Number: NCT03358030

Document Date: Protocol Version 2: 14 June 2018

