3.4 Overall Study Duration and Follow-up

For all cohorts, the Study will consist of a 4-week screening period for procedures after the informed consent is signed. An additional 21 days is permitted prior to screening period for signing of the informed consent. All cohorts will consist of a 26-week Treatment Period, and a 12-week Post-Treatment Evaluation Period. For all cohorts, please refer to the Schedule of Procedures in [Appendix A](#).

Subjects may be required to attend additional visits for monitoring of adverse events (AE) or abnormal investigation results. The frequency of additional monitoring will be determined by the Investigator in consultation with the Sponsor.

If Study Drug is discontinued for any reason, subjects are encouraged to continue their regular assessments for the duration of the treatment period and post-treatment evaluation period, unless subject informed consent is withdrawn.

3.4.1 *Screening*

After signing the informed consent form, subject eligibility for the study will be determined within 4 weeks prior to Study Day 1.

During the screening period, at Study Days S-14 (\pm 3) and S-7 (\pm 3), subjects should receive 2 noncontiguous SC injections of 0.75 mL saline. As with Study Drug, these may be administered immediately after dialysis is completed when blood is returning to the subject but must be within 2 hours after dialysis (within 15 minutes is preferred) to determine tolerability to SC injections.

All women will have a serum pregnancy test done between Study Days S-28 and S-14 that must be resulted prior to dosing on Study Day 1.

All screening lab re-tests should be resulted by the central lab prior to randomization on Study Day 1.

3.4.2 *Treatment*

Eligible subjects will receive study treatment every week for 26 weeks. The treatment period consists of the period from the first Study Drug (ISIS 416858 or placebo) injection to the last injection on Day 176 (Week 26), or early study termination.

3.4.3 *Post-Treatment*

Subjects will have follow-up evaluation visits on Study Week 27 (PK Subgroup only), and for Study Weeks 28, 30, 32, 34, 36, 38 (all subjects), or early study termination. The final study visit will be Study Day 260.

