Baseline for the routine clinical assessments of chemistry and hematology, PD markers, assessment of clotting, PK assessments, vital signs and ECG for the study will be the time-point prior to the first administration of Study Drug and prior to dialysis on Day 1 ([Appendix A](#)). If Day 1 values are not available, screening values will be used. For Urea Reduction Ratio, the blood collections for blood urea nitrogen (BUN) prior to dialysis as well as the post-dialysis sample on Day 1 will be used.

6.1.3 *Treatment Period (Day 1 to Day 176)*

Enrolled subjects may be administered ISIS 416858 or placebo immediately after dialysis is completed (when blood is returning to the subject) but must be within 2 hours (preferably within 15 minutes) approximately once each week for a total of 26 weeks of treatment.

Once-weekly SC administration will occur during Weeks 1 to 26 (Days 1, 8, 15, 22, 29, 36, 43, 50, 57, 64, 71, 78, 85, 92, 99, 106, 113, 120, 127, 134, 141, 148, 155, 162, 169, and 176).

For Study Drug administration on Study Day 1, no dosing window is allowed. For Weeks 2 to 26, a \pm 3-day window may be utilized but Study Drug should be administered each week. Study Drug doses should be administered at least 72 hours apart.

Additionally, no dose of Study Drug will be administered before reviewing a valid platelet result. Valid platelet counts must be conducted every 2 weeks and reviewed prior to dosing. If the platelet result is unavailable (e.g., due to hemolysis, clumping, etc.) from the central lab, a repeat local lab will be conducted and reviewed prior to dosing.

Any questions on study procedures and visit windows may be directed to the Sponsor (or designee).

During all subject contacts, Investigators will check for and record:

- Bleeding events
- AEs
- Concomitant medication changes

Safety and clinical laboratory evaluations as well as PD markers, assessment of clotting, blood sampling, including those for routine PK as well as PK substudy analysis will be performed as indicated in [Appendices A, B, and C](#). Subjects participating in the platelet substudy will have additional blood sampling and processing on Study Days 1, 78, and 176 during the Treatment Period.

Any AEs, including bleeding events, will be recorded. This may include additional information regarding events of interest (i.e., thrombotic events).

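### Subject antibody status, subject incidence and ADA onset ignore whether the Day 1 pre-dose sample was already positive, so pre-existing and treatment-emergent antibody are mixed

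*Combined protocol and SAP*

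**What the plan says.** SAP section 2.8 lists the samples to be tested for antibody: "Samples collected at pre-dialysis/pre-dose on Days 1, 15, 29, 85, 176, and anytime on Day 260", plus early termination samples. Three rules follow.

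- **Positive subject:** "at least one confirmed positive sample result at any time during the treatment or post-treatment evaluation periods".
- **Negative subject:** all evaluated samples in those two periods are negative and "they have at least one evaluable IM result collected post study drug treatment". Anyone else is unknown.
- **Onset:** "Onset in days= The date of first sample has" positive sample status, minus the first dose date, plus 1. The SAP describes this first positive as the start of ADA development.

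None of these rules refers to the Day 1 pre-dose result. That result is used elsewhere in the section. Sample results and titers "before, during, and after treatment with study drug (ISIS 416858 or placebo) (sample IM status) will be listed by treatment and dose", and "The sample IM incidence (number) and incidence rate (percent) at each evaluated study time point" is to be summarized by treatment.

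The transient and persistent classes are optional. They are confined to treatment-induced ADA, a term the SAP does not define.

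Subject IM status supplies the subject-level incidence. It also stratifies the PK summaries (SAP sections 2.7.1 and 2.7.2) and, at the study team's discretion, exposure-response, safety and efficacy summaries.

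**The concern.** An antibody present before the first injection cannot have been caused by it. The trial draws the sample that would separate such subjects, but the subject-level rules do not use it. A subject who is positive on Day 1 before dosing and remains so is counted with subjects who became positive on study, is given an onset date, and enters the IM-positive stratum.

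What is at stake is how two outputs can be read. The subject incidence by treatment cannot be taken as the rate of new antibody, and the onset distribution can contain subjects in whom nothing began. Protocol section 5.2, exclusion 10, admits subjects who have had one earlier dose of a sponsor oligonucleotide, so prior exposure is limited but possible. SAP section 1.7.2 says immunogenicity results arrive after final database lock, so the definitions should be settled before they are seen.

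**Working it through.** The documents state no antibody incidence, baseline prevalence or power for this point, so there is no figure to reproduce. The check is first on the text, then an illustration.

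**1. A subject positive pre-dose on Day 1 and at every later visit.**

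- Status: IM positive, because the Day 15 sample alone satisfies the rule.
- Onset if the pre-dose sample is used: 1 − 1 + 1 = Day 1. The formula itself is not limited to post-dose samples, and the SAP applies the term sample IM status to results before treatment as well.
- Onset if only post-dose samples count: 15 − 1 + 1 = Day 15.
- Persistence: positives from Day 15 to Day 176 span (176 − 15)/7 = 23 weeks, above the 16-week threshold. The subject would be persistent unless the undefined treatment-induced qualifier is applied to exclude the case.

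**2. A subject positive only on the Day 1 pre-dose sample and negative afterwards.**

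- Protocol section 3.4.2: "The treatment period consists of the period from the first Study Drug (ISIS 416858 or placebo) injection". The pre-dose sample lies outside the period, so the subject is IM negative.
- The heading of protocol section 6.1.3 reads "Treatment Period (Day 1 to Day 176". Read by calendar day, the sample lies inside the period, so the subject is IM positive.

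The SAP does not say which reading applies.

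**3. Illustration of size.** Let q be the share of subjects positive before dosing who stay positive, and i the rate of new positivity among the rest. Both are assumptions.

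- Incidence under the written rule = q + (1 − q) × i
- Treatment-induced incidence among all subjects = (1 − q) × i
- Arm sizes from the planned 204: 204/3 = 68 per cohort; 68 × 3/4 = 51 per active dose; 3 × 51 = 153 active; 204 − 153 = 51 pooled placebo.

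With i = 20%:

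| q | Written rule | Treatment-induced | Baseline positives in 153 active | In 51 placebo |
|---|---|---|---|---|
| 0% | 20% | 20% | 0 | 0 |
| 2% | 0.02 + 0.98 × 0.20 = 21.6% | 19.6% | 3.1 | 1.0 |
| 5% | 0.05 + 0.95 × 0.20 = 24% | 19% | 7.7 | 2.6 |
| 10% | 0.10 + 0.90 × 0.20 = 28% | 18% | 15.3 | 5.1 |

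The last two columns are q × 153 and q × 51.

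The share of IM-positive subjects whose antibody was pre-existing is q divided by the written-rule incidence. Over q from 2% to 10% and i from 5% to 30%, it runs from 0.02/0.314 = 6% to 0.10/0.145 = 69%.

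**The case against.** The strongest defence is that the plan contains the means to see the problem. Four stronger readings are tempting, and the documents do not support them.

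- **That the Day 1 result is not used.** It is listed with titers, and the by-time-point summary covers Day 1, so baseline positivity should be visible by treatment. The gap is confined to subject status, subject incidence and onset.
- **That the SAP reports a drug-induced rate.** It does not. The overall figure is called subject IM incidence and is shown by treatment, so the placebo group gives an indirect view of background positivity. Only the description of onset as ADA development implies something new.
- **That the section contradicts itself by using two numerators.** The transient and persistent classes are an optional subset of IM-positive subjects, so a narrower numerator is not a contradiction. The fair criticism is that the narrowing term is undefined. The SAP cites a publication for these classes but does not set out what it means by treatment-induced.
- **That any effect of antibody on PK is diluted.** This is not shown. The PK populations contain only subjects given active drug, so placebo positives cannot enter them. Antibody present during treatment may be the relevant stratifier whatever its origin, and the SAP also allows stratification by titer and onset.

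It is also fair to say that the analysis is descriptive and that the split could be derived later from the listed data. That limits the weight of the point. It does not remove the misclassification in the tables as specified, and the placebo rate cannot identify which active subjects were positive at baseline.

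**Conclusion.** The point holds in a limited form. As written, the subject-level rules count persisting pre-existing antibody as IM positive and give it an onset, on Day 1 or at the first post-dose positive depending on how the formula is read. Subject incidence and the IM strata therefore mix two kinds of antibody, and the term that would separate them is undefined.

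The size cannot be established from the documents. The increases to 21.6%, 24% and 28% rest on assumed baseline rates of 2%, 5% and 10%, on every baseline positive staying positive, and on a 20% rate among the rest. If no subject is positive at baseline, the rates do not differ. This is a minor point of definition. It is worth correcting because the rule can misclassify subjects and the data to avoid that are already planned.

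**What to change.** Amend SAP section 2.8 as follows, before the immunogenicity results are available:

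1. State that the Day 1 pre-dose sample is the baseline and is not part of the treatment period for IM status.
2. Define three groups: baseline-positive; treatment-induced (Day 1 pre-dose negative, later confirmed positive); and treatment-boosted (baseline-positive with a titer rise that the sponsor sets in advance from assay performance). Say how subjects with no evaluable baseline sample are handled.
3. Report each group by treatment, beside the overall IM-positive rate.
4. Compute onset for treatment-emergent cases only, meaning treatment-induced or treatment-boosted, and say which sample dates the onset of a boosted response.
5. Tie the transient and persistent classes to the treatment-induced definition.
6. Keep PK stratification by any-positive status if wanted, with the treatment-emergent split shown beside it.

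The cost is SAP wording and some added table rows. The Day 1 sample and titers are already in the plan, so no new sample, visit or assay is needed.

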1. STUDY INFORMATION

1.1. Protocol and Protocol Amendments

The protocol was amended 1 time. The latest versions of the protocol (Protocol Amendment 1) are provided along with the change summary for the revisions.

Protocol Version	Date	Document Provided
Original	01 June 2017	None
Protocol Amendment 1	14 June 2018	Protocol and change summary
Protocol Amendment 1 for Czech Republic	15 June 2018	Protocol and change summary
Protocol Amendment 1 for Austria	18 June 2018	Protocol and change summary

Notes to File	Date
Pregnancy Test will be Performed Once Every Month for Females of Childbearing Potential in Austria	31 July 2017
Protocol Clarification for Exclusion Criteria #2 and Day 2 Schedule of Procedures	18 December 2017
ISIS 416858-CSS - Blinded Safety Data Reviews	21 June 2018
ISIS 416858-CSS Randomization of Subject- with > 28-day Screening Period for Procedures	26 June 2018
Subject Data: Start Time and End Time of Dialysis Sessions	9 July 2018
ISIS 416858-CSS Protocol Clarification for Pregnancy Re-Testing	16 July 2018
ISIS 416858-CSS Protocol Clarification for Continuing on Study when Study Drug is Discontinued	1 August 2018
Dosing Error Subject- (Randomization-) at Site- (Rand-)	3 August 2018
ISIS 416858-CSS Clarification for Re-Testing of Subjects that have Platelets < 150,000/mm ³ During Screening	22 August 2018
ISIS 416858-CSS FXI Rainin Pipette Calibration Validation Periods	6 September 2018
ISIS 416858-CSS and Enrollment of MYTEMP Patients in Canada	10 September 2018
Unblinding of Lab Data for ISIS 416858-CSS Patient- (Rand-)	1 September 2018
Clarification of Aspirin and/or NSAID Use in Subjects in the Platelet Substudy	24 September 2018
ISIS 416858-CSS FXI Activity and Antigen Levels	19 October 2018
Immediate Change for Shipment Temperature of Hematology Samples (Sites [REDACTED])	28 December 2018
ISIS 416858-CSS Unblinded Local Lab Entity	4 March 2019

Notes to File	Date
Additional Medical Monitoring Requests in Study ISIS 416858-CSS	5 April 2019
ISIS 416858-CSS Per-Protocol Set (PPS)	7 June 2019
ISIS 416858-CSS Disallowed Concomitant Medication and Per-Protocol Set (PPS) Analysis	4 September 2019
ISIS 416858-CSS Study Dmg Intemption or Discontinuation Due to Low Platelets	4 September 2019
ISIS 416858-CSS Data Entry Errors: Date of Dosing	8 October 2019

IONIS PHARMACEUTICALS, INC.

ISIS 416858-CSS

10.6.3	Pharmacokinetic and Immunogenicity Analysis.....	56
10.6.3.1	Pharmacokinetic Analysis.....	56
10.6.3.2	Immunogenicity Analysis	56
10.6.4	Pharmacodynamic Analysis.....	57
10.6.5	Additional Exploratmy Analyses	57
11.	INVESTIGATOR'S REGULATORY OBLIGATIONS	57
11.1	Infolmed Consent.....	57
11.2	Ethical Conduct of the Study.....	58

11.3	Independent Ethics Committee/Institutional Review Board	58
11.4	Subject Confidentiality	58
12.	ADMINISTRATIVE AND LEGAL OBLIGATIONS	59
12.1	Protocol Amendments.....	59
12.2	Study Termination.....	59
12.3	Study Documentation and Storage.....	59
12.4	Study Monitoring	60
12.5	Language.....	60
12.6	Compensation for Injmy	60
13.	REFERENCES	61
14.	APPENDICES.....	63
Appendix A	Schedule of Procedures	64
Appendix B	List ofLaboratory Analytes	69
Appendix C	PK Sampling Schedule	71
Appendix D	Grading Scale for Adverse Events Relating to Laboratory Abnmmalities	73

TABLE OF TABLES

		Page
Table 1	Summaly ofISIS 416858 Clinical Studies.....	25
Table 2	Study Drng Characteristics.....	37
Table 3	Study Drng Dosing Information.....	38
Table 4	Additional Labs to be Perfolmed in the Event of a Platelet Count $< 75,000/\text{mm}^3$	41
Table 5	Clotting Scale	57

TABLE OF FIGURES

		Page
Figure 1	Design of Chimeric 2'-MOE Phosphorothioate Oligonucleotides (MOE-Gapmer)	22

PROTOCOL AMENDMENT

Protocol Number: ISIS 416858-CSS

Protocol Title: A Phase 2, Randomized, Double-Blind, Placebo-Controlled Study of the Safety, Pharmacokinetics, and Pharmacodynamics of Multiple Doses of ISIS 416858 (IONIS-FXhx an Antisense Inhibitor of Factor XI), Administered Subcutaneously to Patients with End-Stage Renal Disease on Hemodialysis

Amendment Number: I

Amendment Date: 14 June 2018

The primary purpose of this amendment is to further clarify certain aspects of the protocol and to simplify procedures for the study site. Other changes will allow study sites to better prepare subjects for the study and provide added flexibility for study subjects with a longer timeframe for signing of the informed consent and greater visit windows, respectively.

Minor changes (not included in the list of changes below) have been made throughout the protocol to correct errors and/or to improve the overall clarity of the original protocol but these changes do not impact subject safety, exposure, or the overall study design.

The following table provides a summary list of major changes to the protocol:

Protocol Section(s)	Description of Change	Rationale
Synopsis Study Design Schema Section 3.4 Section 8.3 Section 8.6 Section 8.7	Clarified that subjects are encouraged to complete the entire treatment and post-treatment evaluation periods, even if Study Drug (ISIS 416858 or placebo) has been discontinued.	In this safety study, it is important to obtain a complete safety set in order to complete an intent to treat analysis. Additional text provides clear expectations for subject and sites.
Exclusion Criteria (Synopsis Section 5.2)	Added to Exclusion Criteria #3 to include FXI activity < 0.3 U/ml at Screening.	Provides clarification on screening laboratory procedures to be evaluated for subject eligibility.
Exclusion Criteria (Synopsis , Section 5.2) Synopsis Section 8.9.1 Concomitant Therapy	For subjects in the optional platelet function substudy, aspirin or NSAIDs use is now allowed.	Removing the disallowed concomitant therapy of aspirin and NSAIDs for the platelet function subgroup will improve recruitment into the substudy with minimal effects expected for study results based on the requirements of the primary platelet function assays selected.

Protocol Section(s)	Description of Change	Rationale
Synopsis Study Schema Section 3.4 Section 4.1 Section 6.1.1 Appendix A	Extended the screening period for signing of the Informed Consent from 28 days to 49 days	Allows study sites to prepare subjects for the study screening procedures in a timely manner at the convenience of the sites and subjects.
Synopsis Section 3.4.1 Section 8.1 Appendix A	Provided additional clarification on the expected completion of dialysis and Study Drug administration.	Provides more details on dialysis completion and when it is appropriate to administer Study Drug.
Synopsis Section 3.1 Section 4.2	Clarified that subjects are also stratified based on their participation in either or both of the substudies (pharmacokinetic and/or platelet substudy) as applicable.	Added language provides necessary details by which stratification is occurring for substudy participants.
Section 2.3.3.2	Added the preclinical toxicology assessments with respect to the proposed dose levels in the study.	Added details of the relative exposures for humans in preclinical toxicology studies.
Section 6.1.3 Section 6.1.4 Appendix A	Added increased window time for visits occurring in the treatment and post-treatment periods.	Reduces subject burden to increase flexibility without affecting subject safety.
Section 9: Serious and Non-Serious Adverse Event Reporting	
Clarified Adverse Event (AE) definition in Section 9.3.1Added adverse drug reaction (ADR) in Section 9.3.2Added Adverse Event of Interest (AEOI) as Section 9.3.4Clarified in Section 9.4.1 that an SAE should be reported electronically whenever possible	Clarifies terms used in the Safety sections of the protocol and required reporting.
Section 9.5.4 Contraception and Pregnancy	Clarification of the expected pregnancy follow-up period was provided.	Clarifies the follow-up for an outcome of pregnancy for subjects.
Appendix A	Clarified that KW assessments will also be recorded on study visits determining URR.	Ensures that 2 measures of dialysis adequacy are evaluated during the study.
Appendix A	Clarified that the 2 additional ECG measures at specified visits are not required. Only 1 ECG measure is required per timepoint for the study.	Reduces subject burden without affecting study results.
Appendix A	Removed the repeat pregnancy testing during screening of women determined to not be of child bearing potential and clarified the testing of women of child-bearing potential.	Reduces subject burden during screening without affecting subject safety and clarifies for site staff the recurrent testing of women of child-bearing potential.

PROTOCOL SYNOPSIS

Protocol Title	A Phase 2, Randomized, Double-Blind, Placebo-Controlled Study of the Safety, Pharmacokinetics, and Pharmacodynamics of Multiple Doses of ISIS 416858 (IONIS-FXIRXan Antisense Inhibitor of Factor XI), Administered Subcutaneously to Patients with End-Stage Renal Disease on Hemodialysis.
Study Phase	2
Indication	Evaluation of the antithrombotic effects of ISIS 416858 in patients with end-stage renal disease (ESRD) receiving chronic hemodialysis.
Primary Objectives	To evaluate the safety, pharmacokinetics (PK), and pharmacodynamics (PD) of ISIS 416858 (200,250, and 300 mg once-weekly) as compared to placebo.
Exploratory Objectives	Incidence of myocardial infarction (MI), stroke, systemic embolism, and cardiovascular (CV) mortality
Study Design	
This is a Phase 2, multi-center, stratified, randomized, double-blind, placebo-controlled study of ISIS 416858 (IONIS-FXIRXan Antisense Inhibitor of Factor XI) treatment for up to 26 weeks in ESRD patients receiving hemodialysis at least 3 times a week.
 
Subjects included in this study will maintain all of their standard of care dialysis treatments (including heparins) as determined by their treating practitioners.
 
Subjects will be stratified based on the diagnosis of documented atrial fibrillation at Screening, and then subjects will be randomized to 1 of 3 dose cohorts in a 1:1:1 ratio (Cohort A, Cohort B, and Cohort C). Additionally, the subjects will also be stratified based on their participation in the substudies (pharmacokinetic and/or platelet substudy) as applicable. Within each dose cohort, subjects will be randomized in a 3:1 ratio to receive subcutaneous treatment with Study Drug (either ISIS 416858 or placebo).
 
Cohorts A, B, and C
 
Patients in Cohort A will be randomized to receive once-weekly either 200 mg ISIS 416858 or placebo, subjects in Cohort B will be randomized to receive either 250 mg ISIS 416858 or placebo, and Cohort C will be randomized to receive either 300 mg ISIS 416858 or placebo.
 
The study will include a 4-week screening period for procedures and a 26-week treatment period followed by a 12-week post-treatment evaluation period. Subjects are encouraged to complete the entire treatment and post-treatment evaluation periods, even if Study Drug (ISIS 416858 or placebo) has been discontinued.
 
Upon completion of screening evaluations, including SC tolerability assessments with 0.9% sterile saline injections, eligible subjects will receive Study Drug weekly for the 26-week treatment period. All doses of Study Drug will be administered subcutaneously (SC) after completion of the hemodialysis treatment. Study Drug can be administered immediately after dialysis is completed when blood is returning to the subject but must be within 2 hours (preferably within 15 minutes of the conclusion of dialysis).

Number of Subjects	Approximately 204 patients are planned to be enrolled in parallel in this study and randomized equally across Cohorts A, B, and C.

PROTOCOL SYNOPSIS *Continued*

Study Population	Inclusion Criteria
	
Inclusion Criteria
 
1. Must have given written informed consent (signed and dated) and any authorizations required by local law and be able to comply with all study requirements.2. Males or females aged 18 to 85 years old at the time of informed consent.
a. Females: must be non-pregnant and non-lactating and either:
i. surgically sterile (e.g., tubal occlusion, hysterectomy, bilateral salpingectomy, bilateral oophorectomy);ii. post-menopausal (defined as 12 months of spontaneous amenorrhea in females > 55 years of age or, in females ≤ 55 years, 12 months of spontaneous amenorrhea without an alternative medical cause and FSH levels in the postmenopausal range for the laboratory involved); or,iii. if engaged in sexual relations and of child-bearing potential, agree to use highly effective contraceptive methods (refer to Section 6.3.1) from the time of signing the informed consent form until at least 84 days (approximately 5 half-lives of ISIS 416858) after the last dose of Study Drug (ISIS 416858 or placebo).b. Males: Surgically sterile or if engaged in sexual relations with a female of child-bearing potential, subject is utilizing an acceptable contraceptive method (refer to Section 6.3.1) from the time of signing the informed consent form until at least 84 days (approximately 5 half-lives of ISIS 416858) after the last dose of Study Drug (ISIS 416858 or placebo).3. End stage renal disease maintained on outpatient hemodialysis at a healthcare center for > 3 months from screening with hemodialysis at least 3-times per week for a minimum of 9 hours per week of prescribed treatment time and plan to continue this throughout the study. 
Exclusion Criteria
 
1. Subjects with a history of a major medical event (e.g., previous acute coronary syndrome, stroke or transient ischemic attack, or systemic thromboembolic event) within 3 months of screening, major surgery within 3 months of screening, or new major physical examination finding (not accounted for by past medical history), except for documented atrial fibrillation.2. Active bleeding (as judged clinically-significant by the Investigator) within the past 3 months from screening or documented bleeding diathesis (excluding uremia), coagulopathy, or recent history of prolonged compression time at arteriovenous fistula.3. Screening laboratory results as follows:
Platelet count < 150,000 cells/mm³
o < 180,000 cells/mm³ for platelet function/activation subgroupINR > 1.4aPTT > upper limit of normal (ULN)FXI activity < 0.3 U/mlALT or AST > 2 x ULNTotal bilirubin > ULN

PROTOCOL SYNOPSIS *Continued*

Study Population Continued	Exclusion Criteria Continued
	
4. Subject is not willing to have weekly subcutaneous injections over the study period as assessed during screening.5. Active infection requiring systemic antiviral or antimicrobial therapy that will not be completed prior to Study Day 1 (first dose) or IV antibiotic use at the time of Screening.6. Unwillingness to comply with study procedures, including follow-up, as specified by this protocol, or unwillingness to cooperate fully with the Investigator.7. Known history of or positive test at Screening for human immunodeficiency virus (HIV), hepatitis C or chronic hepatitis B.8. Malignancy within 5 years, except for basal or squamous cell carcinoma of the skin or carcinoma in situ of the cervix that has been successfully treated. Subjects with a history of other malignancies that have been treated with curative intent and which have no recurrence within 5 years may also be eligible if approved by the Sponsor Medical Monitor (or designee).9. Treatment with another investigational drug, biological agent, or device within 1 month of screening, or 5 half-lives of investigational agent, whichever is longer.10. Any history of previous treatment with an oligonucleotide (including siRNA). Subjects that have previously received only a single-dose of an ISIS-oligonucleotide as part of a clinical study may be included as long as a duration :: 4 months has elapsed since dosing.11. Attending nephrologist answers "no" to the question, "Would you be surprised if this patient died in the next year?"12. Within 6 months prior to screening, have any of the following:
• More than 3 episodes of severe hypoglycemia requiring the assistance of another person to actively administer carbohydrate, glucagon or other resuscitative actions• One (1) event of hypoglycemia in which the patient required hospitalization• Recurrent syncope and recurrent hypotension in the inter-dialytic period requiring intervention13. Planned major surgery in the next 6 months, including subjects receiving a kidney transplant or subjects that anticipate changing dialysis modality (i.e. hemodialysis to peritoneal dialysis).14. Recent history of, or current drug or alcohol abuse as determined by the Investigator.15. Concomitant use of anticoagulant/antiplatelet agents (e.g., warfarin, dabigatran, rivaroxaban, clopidogrel) that may affect coagulation (except low dose aspirin (:5100 mg/day)) during Treatment and Post-treatment Evaluation Periods is not allowed. Stable doses of heparins during dialysis are permitted.16. Uncontrolled hypertension as judged by the Investigator. For example, subjects with a pre- or post-dialysis blood pressure (BP) that is > 180 mmHg on at least 3 of the last 5 dialysis treatments.17. Have any other conditions, which, in the opinion of the Investigator or Sponsor would make the subject unsuitable for inclusion, or could interfere with the subject participating in or completing the study.

[figure not shown]
PROTOCOL SYNOPSIS *Continued*

Treatment Groups	
There will be 3-dose cohorts that will run concurrently. Subjects will be stratified based on the diagnosis of documented atrial fibrillation and then randomized to 1 of 3 dose cohorts in a 1:1:1 ratio (Cohort A, Cohort B, and Cohort C). Within each dose cohort, subjects will be randomized in a 3:1 ratio to receive subcutaneous treatment with either ISIS 416858 or placebo that is added to standard of care hemodialysis therapies as prescribed by their providers, including heparin.
 
Cohort A: Approximately 68 dialysis subjects will be randomized 3:1 to either 200 mg ISIS 416858 or placebo
 
Cohort B: Approximately 68 dialysis subjects will be randomized 3:1 to either 250 mg ISIS 416858 or placebo
 
Cohort C: Approximately 68 dialysis subjects will be randomized 3:1 to either 300 mg ISIS 416858 or placebo

Study Drug Dosage and Administration	
The SC Tolerability assessments using 0.9% sterile saline should be administered as two 0.75 ml noncontiguous injections on Study Days S-14 (\pm 3) and S-7 (\pm 3).
 
For Cohort A, B and C, the Sponsor will provide ISIS 416858 (200 mg/ml, 1.0 ml) and Placebo (1.0 ml). All doses are given by SC injection.
 
Study Drug will be administered SC post-dialysis at any time from when blood is being returned to the subject but must be within 2 hours (preferably within 15 minutes of dialysis conclusion) for a total of 26 consecutive weeks of treatment in all cohorts.
 
The injection volume will be 1.0 ml for Cohort A (200 mg), 1.25 ml for Cohort B (250 mg) and 1.5 ml for Cohort C (300 mg). Cohorts B and C will be administered Study Drug (ISIS 416858 or placebo) as 2 noncontiguous SC injections.

Rationale for Dose and Schedule Selection	Based on the PK/PD profile of ISIS 416858 in the previous Phase 1 (ISIS 416858-CS1) and Phase 2 (ISIS 416858-CS3 and ISIS 416858-CS4) studies, doses up to 300 mg of ISIS 416858 have demonstrated significant reduction in FXI activity and consequent anti-thrombotic effects without an increased bleeding risk.
Study Visit Schedule and Procedures	
Detailed information regarding the study procedures is outlined in protocol Section 6, and Appendices A and C.
 
The study period for an individual patient consists of signing the informed consent up to 7-weeks (Day -49) prior to randomization, an approximately 4-week screening period for procedures, a 26-week treatment period during which Study Drug (ISIS 416858 or placebo) will be administered SC once-weekly, and a 12-week post-treatment evaluation period.
 
During the screening period, subjects who give written informed consent will undergo a medical history and comprehensive physical examination and have blood samples taken for clinical laboratory testing. Additional tests include a coagulation panel consisting of aPTT, PT/INR, FXI antigen and activity levels. For Screening Days S-14 (\pm 3 days) and S-7 (\pm 3 days), subjects shall receive 2 noncontiguous SC injections of 0.75 ml saline to determine tolerability to SC injections.
 
During the treatment period, Study Drug (ISIS 416858 or placebo) will be administered as a SC injection once during Weeks 1 (Day 1), 2, 3, 4, 5, 6, 7, 8, 9, 10, 11, 12, 13, 14, 15, 16, 17, 18, 19, 20, 21, 22, 23, 24, 25, and 26.
 
Collection and measurement of vital signs, clinical laboratory parameters (including hematology, serum chemistry, coagulation, immunogenicity, and inflammatory markers), adverse events (including bleeding events), and concomitant medication will be performed according to the schedule of procedures in Appendix A for both treatment and post-treatment evaluation periods. Following the Week 26 visit, subjects will enter the 12-week post-treatment evaluation period.

PROTOCOL SYNOPSIS *Continued*

